### 10.2. Baseline

Baseline (first day of crenolanib) should be performed as follows:

1. Chemistry panel including total bilirubin, ALT and AST should be collected within 24 hours of initiation of crenolanib. Eligibility criteria (Section 7.1.7) should be reconfirmed at this time point. If patient does not have normal total bilirubin and ALT/AST  $\leq 2x$  ULN at this time point, crenolanib can be delayed until these criteria are met (section 1 overview of treatment plan).
2. Baseline EKG should be collected after completion of chemotherapy (within 24 hours of start of crenolanib) and a second EKG should be performed 2 hour ( $\pm$  30 minutes) post first dose of crenolanib
3. Active concomitant medications within 24 hours of initiation of crenolanib
4. CBC with differential collected after completion of chemotherapy and prior to initiation of crenolanib
5. PS, Physical exam with vitals after completion of chemotherapy and prior to initiation of crenolanib
6. Active toxicities or medical conditions after completion of chemotherapy and prior to initiation of crenolanib

7. Blood and marrow samples for translational research including pharmacokinetic analysis will be obtained as defined in Section 11 and lab manual. Every effort should be made to collect correlative studies at all time points for all patients; however, missing collection in one or more of these time points will not be considered a protocol deviation/violation.

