### **13.8. Safety Analyses**

All subjects will be evaluable for safety. Adverse events that occur after a subject is entered (signs informed consent), but before the patient receives study drug, will not be recorded on the CRF unless the investigator believes that the events may have been caused by a protocol procedure. Safety analyses will include summaries of the incidence of adverse events by maximum CTCAE

grade (version 4.03; NCI 2010) that occur during the study treatment period or within 30 days of the last dose of study treatment or until alternate therapy is started, regardless of causality or relatedness to study drug. The safety-related outcomes that will be summarized include:

- Adverse events,
- TEAEs,
- SAEs,
- Deaths,
- Discontinuations due to adverse events,
- Extent of exposure to study drug treatment,
- Hospitalizations,
- Use of key concomitant medications.

Analyses for data with discrete dates (for example, death date and start/stop dates of concomitant medications) will be performed through 30 days after the patient has been discontinued from study treatment or until alternate therapy is started. Adverse events will also be analyzed in this time frame. After 30-day post-discontinuation follow-up, only those SAEs that are thought to be related to study treatment or protocol procedure should be reported immediately to AROG or its designee. For these events, the patient must be followed until the event has resolved or stabilized.

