#### **14.4. Adverse Event Reporting**

AROG has standards for reporting AEs that are to be followed regardless of applicable regulatory requirements that may be less stringent. Lack of drug effect is not an AE in clinical trials, because the purpose of the clinical trial is to establish drug effect.

Adverse Events (AEs) will be evaluated according to CTCAE version 4.03 and documented in medical record. After the Informed Consent Document (ICD) is signed, study site personnel will record the occurrence and nature of each patient's pre-existing conditions, including clinically significant signs and symptoms of the disease. During the study, site personnel will record any change in the pre-existing condition(s) and the occurrence and nature of any new adverse events.

All AEs related to protocol procedures are reported to AROG or designee. All AEs occurring after the patient receives the first dose of study drug must be reported to AROG or its designee via CRF. Investigators will be instructed to report to AROG or its designee their assessment of the potential relatedness of each AE to protocol procedure, studied disease state, study drug, and/or drug delivery system via CRF.

For all AEs, the investigator should specify:

1. ***Seriousness:*** Seriousness of an AE is defined by the criteria described in Section 10.1. A severe AE should not always be considered as serious.
2. ***Date of onset and its duration (start and end dates):*** The investigator should follow up the outcome of any AEs until they return to normal or consolidation of the subject's condition. All adverse events still evolving at the end of the study are to be followed up by the investigator until their resolution or stabilization.
3. ***Severity:*** (using NCI CTCAE v.4.03),

4. **Action taken with respect to study drug:** (no action taken; study drug dosage adjusted/temporarily interrupted; study drug permanently discontinued due to this adverse event; hospitalization/prolonged hospitalization), corrective treatment/therapy given, additional investigations performed
5. **Outcome:** Resolved/Recovered, recovering/resolving, not recovered/resolved, recovered/resolved with sequelae, unknown
6. **Relatedness:** If an AE is related or not related to study drug

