### **14.5. Serious Adverse Event Reporting**

Serious adverse event collection begins after the patient has signed informed consent and has received a tablet or more of study drug. If a patient experiences an SAE after signing informed consent, but prior to receiving study drug, the event will NOT be collected unless the investigator feels the event may have been caused by a protocol procedure.

In case of a SAE, the investigator, within 24 hours of learning of the SAE or subject death, must notify the sponsor (Arog Pharmaceuticals by e-mail: [contact] or [contact]) and transmit the following information (within a signed SAE report form):

- Subject identification code, demographics and vitals
- Description of event with onset and duration (with CTCAE event term & severity)
- Dates, dose and frequency of study drug administered
- Assessment of the seriousness and causality of the event with the study drug using the causality criteria (EVCTM): related versus not related
- Study drug status (dose interrupted or discontinued)
- Date of death (if applicable)
- Concomitant therapy and interventions
- Pertinent laboratory data/diagnostic tests
- Pertinent medical history including underlying diagnosis

All SAEs must be followed by the investigator until resolution or stabilization until the subject's death. This may mean that follow-up will be extended beyond the subject's withdrawal from the trial. The investigator must provide follow-up information (outcome, more precise medical details, results of investigations, copy of discharge summary, etc...) within 24 hours of information becoming available to Arog Pharmaceuticals and to the study monitor, again using the SAE Report Form indicating follow-up. When this information is passed on, care must be taken to continue to respect subject anonymity. The study monitor may contact, or visit the investigator, in order to obtain details of the event.

The sponsor will report all SUSAR to the country specific regulatory authorities within the request period. The evaluation of expectedness is based on knowledge of the adverse reaction on the reference document: the current reference document is the latest version of the Investigator's Brochure of crenolanib.

The sponsor will also inform the IRB of any SAE with the potential to modify the benefit/risk ratio of the present study. The sponsor will be responsible for reporting of New Safety Issues and Annual Safety Reports to IRBs.

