#### **14.6. Follow-up of Adverse Events**

All adverse events will be followed up according to Good Clinical Practice.

**During Treatment:** During study, site personnel will track any change in the condition(s) and the occurrence and nature of any AEs and record the highest grade of the adverse event per cycle on the CRF. CTCAE grading will be assigned before each visit for any adverse events experienced during the previous visit period.

**Preparation for transplant:** Once patient enters conditioning prior to transplant, crenolanib will be held (72 hours prior to start of conditioning). Patients will not be followed for safety once conditioning starts. If patient receives maintenance crenolanib following transplant, safety will be assessed once patient restarts crenolanib (per protocol).

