## II. Consolidation

Assessment	Baseline - Consolidation 1-4	On Treatment - Consolidation 1-4
Day	First day of HiDAC consolidation	First day of crenolanib
Prior/Concomitant medications and significant non-drug therapies	X	X
Physical examination with ECOG PS	X	X
EKG a		X*
Vitals and Weight	X	X
Assessment of adverse events, toxicities	X	X
Hematology (CBC with differential) c	X	X
Serum Chemistries (CMP with bilirubin, ALT/AST and creatinine) c	X	X +
Urine or serum pregnancy test		Every 6 months while patient is on study
Blood collections for PK and correlative sciences b		X*
Bone marrow biopsy and aspirate d		Per SOC

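### Adverse events on the chemotherapy days of Induction 1 are generally not recorded, while those of later courses are reportable, and Section 13.8 pools the two; separate summaries are a cheap improvement

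*Combined protocol and SAP*

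**What the plan says.** **When recording starts.** Under Section 13.8, events after consent but "before the patient receives study drug, will not be recorded on the CRF unless" the investigator thinks a protocol procedure may have caused them. Section 14.4 adds: "All AEs occurring after the patient receives the first dose of study drug must be reported to AROG or its designee via CRF". Section 14.5 sets the same start for serious events: "Serious adverse event collection begins after the patient has signed informed consent and has received a tablet or more of study drug". Study drug means crenolanib, because Section 8.3 counts cycle days from chemotherapy and distinguishes that from study drug.

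**What counts as baseline.** Section 10.2 places baseline on the first day of crenolanib and collects "Active toxicities or medical conditions after completion of chemotherapy and prior to initiation of crenolanib". The definition of a treatment-emergent event in Section 4 requires onset or worsening after baseline.

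**Later courses.** Section 10.3 item 1b schedules consolidation adverse event documentation from Day 1 of crenolanib and then per local practice. Appendix IV, part II, has an earlier assessment column, headed "First day of HiDAC consolidation".

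**How events are kept and summarised.** Section 14.6 tells sites to "record the highest grade of the adverse event per cycle on the CRF", and a cycle begins with chemotherapy (8.3, 10.3). Section 13.8 then plans incidence by maximum grade, irrespective of cause, over the treatment period plus 30 days. Section 13.1.1 provides for analysis by cohort and for some pooling of cohorts, but not for a split by treatment phase.

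**The concern.** The recording trigger is tied to the patient, whereas chemotherapy recurs with each course. In Induction 1 the trigger falls after chemotherapy has finished. In every later course it has already been met. Read with 14.4, a Day 6 mucositis would go unrecorded in Induction 1 and, if still active at baseline, would be entered as a baseline condition. The same event in re-induction would be a reportable treatment-emergent event.

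Safety of crenolanib given sequentially with chemotherapy is a primary objective. The pooled incidence describes neither of the two quantities a reader might want. It is not the toxicity of the whole regimen, because the first chemotherapy block is missing. It is not the toxicity of the crenolanib periods, because later chemotherapy blocks are included.

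**Working it through.** **1. Reproduce the start days.** Induction cytarabine runs on Days 1–7 (Tables 2 and 3), and crenolanib follows 24–48 hours later with a +7-day window (8.2.1).
- Earliest start: 7 + 1 = Day 8, or 7 + 2 = Day 9. Section 5.8 states Day 9, which agrees.
- End of window: 9 + 7 = Day 16. This agrees with the Day 16 point in 8.2.1, beyond which a delay needs discussion with the sponsor. It is not an absolute limit.
- Consolidation cytarabine is given on Days 1, 3 and 5 (8.2.2): 5 + 2 = Day 7, and 7 + 7 = Day 14, which agrees with the Day 14 point given there.

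**2. Induction 1 days before recording starts** = first crenolanib day − 1.
- Day 8 start: 7 days. Day 9 start: 8 days. Day 16 start: 15 days.
- In each case all 7 chemotherapy days fall outside recording, apart from the protocol-procedure exception.

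**3. Share of the cycle.** The plan fixes no cycle length for induction. Taking 28 and 42 days as assumptions, from the assessment visits:
- Day 9 start: 8/42 = 19% to 8/28 = 29%.
- Day 16 start: 15/42 = 36% to 15/28 = 54%.

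These are shares of days, not of events. Cycles may run longer, which lowers them.

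**4. Later courses under 14.4.** The first dose has already been taken, so 0 of 7 chemotherapy days in re-induction and 0 of the 5 days of the HiDAC block are outside the reporting rule. The 72-hour crenolanib hold before chemotherapy normally keeps those days inside the 30-day window of 13.8. Where the plan wants safety follow-up to stop during other chemotherapy it says so: Section 14.6 does this for transplant conditioning and has no such provision for re-induction or HiDAC.
- One induction only: 0 of 1 chemotherapy blocks reportable.
- One induction and four consolidations: 4 of 5 blocks reportable.

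**5. Reportable is not the same as ascertained.** Set side by side, the passages on consolidation differ. Section 14.4 makes every event after first dose reportable. Section 10.3 item 1b schedules documentation from Day 1 of crenolanib. Appendix IV, part II, has an assessment on the first day of HiDAC, but in a baseline column, and its notes tie local-practice visits to the time on crenolanib. Chemotherapy-day events in consolidation are therefore captured unevenly. In Appendix IV, part I, the first adverse event assessment is on the first day of crenolanib, which matches 13.8.

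**6. From days to rates.** This step cannot be done. The documents give no timing of events within a course.

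**The case against.** **The recording rule is not settled.** Section 13.8 excepts events that a protocol procedure may have caused, and the protocol specifies 7+3. Section 14.1.1 says that every adverse event must be recorded, whatever its grade. This stands as far as it goes: the text conflicts, and reading the Induction 1 days as unrecorded is the natural reading of 13.8, 14.4 and 14.5 but not the only one. If some sites counted 7+3 as a protocol procedure and others did not, capture in Induction 1 would vary by site. That would not remove the problem.

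**Later courses may not be fully covered.** A reader might infer complete capture in every later chemotherapy block. Section 10.3 item 1b and the Appendix IV notes do not support that. The rule makes these events reportable, but the visit schedule does not ensure that they are found.

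**Nothing is planned by cycle.** A reader might infer that by-cycle rates would be distorted. The per-cycle maximum in 14.6 is a CRF instruction, and 13.8 specifies no per-cycle rate. The documents support only the point about the pooled summary.

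**More courses mean more events anyway.** This is correct. Part of the excess in patients with more courses would appear even with Induction 1 fully recorded, and 13.8 lists extent of exposure. Only the part due to the unequal window belongs to this point.

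**No decision changes.** The toxicity stopping rules in 13.2.2 and 13.2.3 count grade 4 crenolanib-related events, which should not arise before crenolanib. The trial is descriptive and single-arm. This limits the importance of the point.

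**A separate SAP is promised in 13.1.** It could add the split, but it cannot restore events, grades or dates that the CRF did not collect.

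**Conclusion.** The point holds as a cheap improvement to a primary-objective summary. Under 13.8, 14.4 and 14.5, events on the 7 chemotherapy days of Induction 1 are generally not recorded, while those on the chemotherapy days of re-induction and consolidation are reportable, with uneven ascertainment in consolidation. The pooled incidence by maximum grade therefore mixes two recording windows.

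The size that can be stated is 8 unrecorded days for a Day 9 start and 15 for a Day 16 start. The percentages depend on assumed cycle lengths. The bias in any adverse event rate is not known. The conclusion assumes that study drug means crenolanib and that sites do not treat 7+3 as a protocol procedure. The documents do not support the inference that the stopping rules for crenolanib-related toxicity or a planned by-cycle comparison are compromised.

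**What to change.** 1. Reconcile Sections 10.3, 13.8, 14.1.1, 14.4 and 14.5 and Appendix IV, part II, into one stated adverse event recording window. Say whether 7+3 and HiDAC count as protocol procedures.
2. In 13.8, alongside the overall incidence, summarise events separately for Induction 1 (from first crenolanib dose), Induction 2, consolidation and maintenance. Within Induction 2 and consolidation, split by onset before or after crenolanib resumes, using the onset dates that 14.4 already requires.
3. Base the crenolanib safety statement on the crenolanib periods, noting that visit schedules still differ by phase. If the window stays as it is, state in the table notes that the chemotherapy days of Induction 1 were not recorded.
4. Keep grade by dated event record. A per-cycle maximum alone cannot show whether the worst grade arose before or after crenolanib resumed.

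The cost is extra tables and a CRF clarification. No new visits are needed.

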### **7.4. Discontinuations**

#### **7.4.1. Discontinuations of Study Drugs and Disease status/Survival Follow up of Patients**

The criteria for enrollment must be followed explicitly. If a patient who does not meet enrollment criteria is inadvertently enrolled, that patient should be immediately discontinued from the study drug.

Study drug may be held for an extended period of time for comorbidities including but not limited to infections, ICU admissions, severe graft vs host disease, and other comorbidities typically seen in patients undergoing induction, consolidation or allogeneic transplant therapies for AML. Such prolonged drug hold will not require the patient to be taken off study. Study drug can be restarted, even after prolonged drug holds, at the same dose as was last received by the patient. Restart of study drug will require a discussion with the sponsor.

Study drug may be held for an extended period of time if requested by the patient without necessitating the patient to be taken off study. Study drug can be restarted, even after prolonged drug holds, at the same dose as was last received by the patient. Patients will be continued to be followed for survival and disease status per protocol. Safety will be followed as per section 14.

Patients, who for any reason, require treatment with another therapeutic agent for AML or investigational agent will be discontinued from the study drug prior to introduction of the new agent. Restart of study drug will require a discussion with the sponsor.

Patients who have disease refractory to induction or consolidation therapy will be taken off crenolanib but be followed for survival. Similarly, patients who relapse after achieving a response will be taken off crenolanib but be followed for survival.

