**13.2.1. Excessive early mortality**

Early stopping rules for excessive mortality will be applied in the safety phase of the study. Early mortality is defined for this study as death due to any cause within 30 and 60 days of the initiation of study treatment. In the VALOR trial, all-cause mortality rates of 7.9% and 19.7% were reported, respectively, for patients with relapsed/refractory AML who received cytarabine and placebo as induction therapy. [14] The 30-day mortality rate of 7.9% from the VALOR trial is similar to the 28-day mortality rate of 10.3% that was reported from a retrospective analysis of more than 3000 patients with newly diagnosed AML, the majority of whom were treated with cytarabine-based regimens as induction therapy.[11]

Based on the above considerations, enrollment in a cohort will be halted if the observed 30- and 60-day early mortality rate exceeds 10% and 20%, respectively, as follows: if 1 or more of the first 6 patients enrolled within a cohort die prior to Day 30 then enrollment of additional patients within that cohort will be halted pending review by the Protocol Safety Committee. Additionally, enrollment will be halted within a cohort if 2 or more of the patients die prior to Day 60. Otherwise, 6 additional patients will be enrolled within the cohort provided none of the other stopping criteria have been met.

For the second group of 6 patients within a cohort, if 2 or more of the patients enrolled within a cohort die prior to Day 30, then enrollment of additional patients will be halted pending review by the Protocol Safety Committee. Similarly, if 3 or more of the patients enrolled within a cohort die

prior to Day 60, then enrollment of additional patients will be halted for that cohort. If these and the other early stopping criteria are not met, then the 12 additional patients will be enrolled within the cohort.

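### The Section 13.8 window on death dates lets the safety summary omit deaths that Section 13.2.1 counts as early mortality, mainly in the 60-day figure

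*Combined protocol and SAP*

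**What the plan says.** Section 13.8 (Safety Analyses) names deaths as one of the outcomes to be summarised. It then sets a window for dated data and gives the date of death as its first example. Such analyses "will be performed through 30 days after the patient has been discontinued from study treatment or until alternate therapy is started". The same period is set for adverse events. Nothing in 13.8 exempts deaths or early mortality.

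Section 13.2.1 runs on a different clock: "Early mortality is defined for this study as death due to any cause within 30 and 60 days of the initiation of study treatment". It has no cut-off at discontinuation or at new therapy. The limits are that "enrollment in a cohort will be halted if the observed 30- and 60-day early mortality rate exceeds 10% and 20%, respectively", and they are set beside all-cause rates of 7.9% (30 days) and 19.7% (60 days) from a cited trial in relapsed/refractory AML.

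Section 7.4.1 describes patients to whom both rules apply: "Patients who have disease refractory to induction or consolidation therapy will be taken off crenolanib but be followed for survival". Section 3.2 (Planned Duration of Treatment) also requires survival information after the drug is stopped. Section 13.9, however, takes a patient off study at the earliest of several events, one of which is the start of a new therapy.

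Section 13.3.1, on safety monitoring in the expansion phase, specifies no early-mortality analysis. Overall survival is a secondary objective (6.2), and time-to-event endpoints are summarised by cumulative incidence and Kaplan-Meier methods as appropriate (13.1.1).

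**The concern.** One rule counts forward from the start of treatment. The other stops counting at a point fixed by when treatment ends or changes. A patient who stops early can meet the 13.2.1 definition of a 60-day death and still be missing from the 13.8 summary.

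The omission is not random. It falls on patients whose disease did not respond or who could not tolerate treatment and moved on, which is where early deaths are most relevant to a safety assessment. Safety and tolerability is a primary objective, so the death table in the safety section will be read as the trial's early mortality unless another table is provided.

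**Working it through.** **The plan's own figures.** The 13.2.1 halting counts are the smallest whole numbers whose rate exceeds the limit: floor(n × limit) + 1. The second look is read as cumulative over 12 patients.

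- Day 30, limit 10%: n = 6 gives 1 (16.7%); n = 12 gives 2 (16.7%).
- Day 60, limit 20%: n = 6 gives 2 (33.3%); n = 12 gives 3 (25.0%).

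All four match the text, for example "if 1 or more of the first 6 patients enrolled within a cohort die prior to Day 30" and "enrollment will be halted within a cohort if 2 or more of the patients die prior to Day 60". The stopping rule is internally consistent and uses its own definition of death.

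**Which early deaths the 30-day limb can exclude.** Let Day 1 be the start of study treatment, s the day of discontinuation and d the day of death. The death is outside the 13.8 window if d > s + 30.

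- Deaths by Day 30: s is at least 1, so s + 30 is at least 31. No death by Day 30 can be excluded.
- Deaths by Day 60: exclusion needs s + 31 ≤ 60, so s ≤ 29. The earliest such death is on Day 32.
- With days counted from chemotherapy and the first crenolanib dose on Day 9 (Section 5.8), a patient who stops after that dose leaves the window on Day 39. Deaths on Days 40-60 are excluded. With a first dose on Day 16, they are Days 47-60.

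**Which deaths the alternate-therapy limb can exclude.** Any death after other therapy begins is excluded, whatever the day. The response marrow is taken on Days 14-28 (10.3). A patient found refractory, taken off crenolanib, started on other therapy on Day 25 and dying on Day 45 is a 60-day death under 13.2.1 and outside 13.8. This is the only route by which a Day-30 death can be lost, and after a Day 14-28 marrow it is a narrow one.

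**Possible size.** The inputs are the reference rates in 13.2.1. The difference, 19.7% − 7.9% = 11.8%, is the share of patients dying between Day 30 and Day 60. In 120 patients that is 0.118 × 120 = 14.2 deaths. The documents do not give the fraction f of these that falls outside the window. Assume f between 10% and 50%:

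- Deaths omitted of 120: 14.16 × 0.10 = 1.4, up to 14.16 × 0.50 = 7.1.
- Reported 60-day mortality: 19.7% − 0.10 × 11.8% = 18.5%, down to 19.7% − 0.50 × 11.8% = 13.8%.

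**The case against.** The best defence is that the two sections do different jobs. Section 13.2.1 is a self-contained stopping rule that the Protocol Safety Committee applies in the safety phase. Section 13.8 describes on-treatment safety summaries. All deaths are then captured under overall survival, and Day-30 and Day-60 mortality could be read from that curve. Most of this stands, and it rules out three stronger readings that a reader might infer.

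- *That the stopping rule is weakened.* One lost death would turn 3/12 (25.0%) into 2/12 (16.7%), under the 20% limit. But no sentence applies the 13.8 window to the 13.2.1 counts.
- *That the expansion phase and the pooled 120 have no other mortality analysis.* Overall survival is one. What is missing is a specified early-mortality figure at Day 30 and Day 60.
- *That the response rates in 13.1.2 give the number affected.* Rates of 66-69% and 74-76% imply 24-34% non-responders, or 29-41 of 120. These are not all early stoppers. Section 8.2.1 allows a second induction under the protocol, which is not alternate therapy, and some non-responders may die on treatment, inside the window.

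Two further points are fair. The 19.7% comes from relapsed/refractory patients and is not a forecast for newly diagnosed AML. Also, 13.8 does not say that the earlier of its two limits applies, although 14.6 does for safety follow-up; that is the natural reading but is not stated.

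The defence does not account for 13.8 naming death date as its own example without exempting early deaths. Nor is the survival curve a complete backstop, because the 13.9 off-study rule sits uneasily with survival follow-up after new therapy.

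**Conclusion.** The concern holds as a gap in the safety reporting. As written, 13.8 allows the summary of deaths to omit early deaths as 13.2.1 defines them. The 60-day figure is exposed through both limbs, the Day-30 figure only through the start of other therapy. The stopping rule and the overall survival analysis are not shown to be affected.

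The size cannot be derived from the documents. The range of 18.5% to 13.8% in place of 19.7% rests on the protocol's reference rates applying here and on the assumed 10-50% share of Day 30-60 deaths outside the window. The exact days also depend on whether study treatment starts with chemotherapy or with crenolanib, which 13.2.1 does not say. The correction is worth making because it is cheap and bears on a primary objective.

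**What to change.** 1. In 13.8, remove death date from the window and keep the window for adverse events and concomitant medications.
2. Add all-cause Day-30 and Day-60 mortality, by anthracycline and overall, irrespective of discontinuation or new therapy.
3. Use the 13.2.1 clock for this table, and state whether initiation of study treatment means first chemotherapy or first crenolanib dose. The choice matters: 8.3 counts cycle days from chemotherapy, while the Appendix IV induction key allows for screening while induction chemotherapy is under way.
4. Show deaths within 30 days of last dose as an additional on-treatment row.
5. Reconcile the off-study rule in 13.9, which includes the start of a new therapy, with the survival follow-up in 3.2 and 7.4.1, so that the dates needed for item 2 are collected.

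The cost is a few sentences in 13.8, 13.2.1 and 13.9, carried into the separate SAP foreseen in 13.1, plus a short table. Treatment does not change, and survival follow-up after discontinuation is already planned. The downside is that the reported early mortality may be slightly higher.
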